#### 3.1.2. Primary Immunogenicity Endpoints

In participants complying with the key protocol criteria (evaluable participants), at the following time point after receipt of study intervention:

• 1 month after Dose 2.

Below are the primary immunogenicity endpoints:

• SARS-CoV-2 serum neutralizing titers.

Titers above the LLOQ are considered accurate and their quantitated values will be reported. Values below the LLOQ, denoted as BLQ, will be set to  $0.5 \times$  LLOQ for analysis. However, this calculation may be adjusted based upon additional data from the assay. LLOQ results will be included in the analysis specification once they are available.

#### 3.2. Secondary Immunogenicity Endpoints

In evaluable participants, at the following time points:

• Baseline, 21 days after Dose 1; 7 and 14 days and 6 and 12 months after Dose 2.

Below are the secondary immunogenicity endpoints:

• SARS-CoV-2 serum neutralizing titers.

Also, secondary immunogenicity endpoints will be described in healthy Japanese evaluable participants with/without confirmed COVID-19 before Dose 2 at the following time points:

• Baseline (only for GMTs), 21 days after Dose 1; 7 and 14 days and 1, 6, and 12 months after Dose 2.

Participants "with confirmed COVID-19 before Dose 2" for the subgroup analysis in the protocol are defined as those who reported confirmed COVID-19 diagnosis as an AESI by Visit 4 (clinical laboratory subset) or Visit 2 (standard participants) in Section 3.1.1.4.

#### 3.3. Other Endpoints

# 3.3.1. Exploratory Immunogenicity Endpoints

Exploratory immunogenicity endpoints will be described in healthy evaluable Japanese participants with/without confirmed COVID-19 during the study at the following time points after receipt of study intervention:

• Baseline (only for GMTs), 21 days after Dose 1; 7 and 14 days and 1, 6 and 12 months after Dose 2.

Participants "with confirmed COVID-19 during the study" for the subgroup analysis in the protocol are defined as those who reported confirmed COVID-19 diagnosis as an AESI by Visit 9 (clinical laboratory subset) or Visit 7 (standard participants) in Section 3.1.1.4.

Below are the immunogenicity endpoints:

- SARS-CoV-2 serum neutralizing titers.
- SARS-CoV-2 N-binding antibody assay.

A positive SARS-CoV-2 N-binding antibody result after vaccination in a participant with a negative SARS-CoV-2 N-binding antibody result at baseline will be considered seroconversion to SARS-CoV-2.

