### 8.13.1. Potential COVID-19 Illness Visit (Optimally Within 3 Days After Potential COVID-19 Illness Onset)

This visit is expected to involve the sharing of healthcare information and services via telecommunication technologies (eg, audio, video, videoconferencing software) remotely, thus allowing the participant and investigator to communicate on aspects of clinical care.

As a participant's COVID-19 illness may evolve over time, several contacts may be required to obtain the following information:

- Record AEs, as appropriate as described in Section 8.3.
- Confirm details of any of the prohibited medications specified in Section 6.5.1 received by the participant if required for his or her clinical care.
- Collect local test results of COVID-19 and local diagnosis of COVID-19 as available.
- Complete the source documents.
- The investigator or an authorized designee completes the CRFs.

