#### 8.15. SARS-CoV-2 NAAT Results From Vaccination 1 and Vaccination 2 Visits

Nasal (midturbinate) swabs for SARS-CoV-2 NAAT are obtained at Visits 1 and 4 (clinical laboratory subset) or Visits 1 and 2 (standard participants) to describe the immune responses elicited by a prophylactic BNT162b2 vaccine in participants with or without confirmed COVID-19 before Dose 2 and during the study (the secondary and exploratory objectives).

Research laboratory—generated positive results from the Vaccination 1 and Vaccination 2 visit swabs will be provided to the site once available, but this will not be in real time. The investigator must report the positive result to the community health center according to the local regulation in Japan.

Participants who have a positive SARS-CoV-2 NAAT result prior to the Vaccination 2 visit (Visit 2 for standard participants, Visit 4 for the clinical laboratory subset) should be handled as follows:

- Positive SARS-CoV-2 test with no symptoms, either at Visit 1 or any time between Visit 1 and the Vaccination 2 visit: A positive test in an asymptomatic participant does not meet exclusion criterion 5; therefore, Vaccination 2 should proceed as normal.
- Confirmed COVID-19 (ie, symptoms and positive SARS-CoV-2 test): This meets exclusion criterion 5; therefore, Vaccination 2 should not be given but the participant should remain in the study.

## 8.16. Procedures for Administration of BNT162b2 to Those Originally Assigned to Placebo After Approval of Protocol Amendment 3

All participants will be contacted by the site and unblinded to study intervention allocation to allow placebo recipients the opportunity to receive BNT162b2 as part of the study. Visit 101 could occur at the same time as the original Visit 8 for the clinical laboratory subset or

Visit 6 for the standard participants, if the participants originally received placebo and want to receive BNT162b2.

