To describe the immune responses elicited by a prophylactic BNT162 vaccine in healthy Japanese adults	
 
In participants complying with the key protocol criteria (evaluable participants):
 
GMTs 1 month after Dose 2
 
GMFR from before vaccination to 1 month after Dose 2
 
	•	SARS-CoV-2 serum neutralizing titers
Secondary Immunogenicity:			
To describe the immune responses elicited by a prophylactic BNT162 vaccine in healthy Japanese adults	
 
In the evaluable participants, at baseline, 21 days after Dose 1; 7 and 14 days and 6 and 12 months after Dose 2:
 
GMTs at each time point
 
GMFR from before vaccination to each subsequent time point after vaccination
 
	•	SARS-CoV-2 serum neutralizing titers
To describe the immune responses elicited by prophylactic BNT162 vaccine in participants with/without confirmed COVID-19 before Dose 2	
 
In evaluable participants, at baseline,
 
21 days after Dose 1; 7 and 14 days
 
and 1, 6 and 12 months after Dose 2:
 
GMTs at each time point
 
GMFR from before vaccination to each subsequent time point after vaccination
 
	•	SARS-CoV-2 serum neutralizing titers
Exploratory Immunogenicity:	·		
To describe the immune responses elicited by prophylactic BNT162 vaccine in participants with/without confirmed COVID-19 during the study	
 
In the evaluable participants, at baseline, 21 days after Dose 1; 7 and 14 days and 1, 6, and 12 months after Dose 2:
 
GMTs at each time point
 
GMFR from before vaccination to each subsequent time point after vaccination
 
	•	SARS-CoV-2 serum neutralizing titers
To evaluate the immune response (non-S) to SARS-CoV-2 in participants with/without confirmed COVID-19 during the study		•	SARS-CoV-2 N-binding antibody

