## 3.1.1.4. Adverse Events

AEs will be assessed from the time of informed consent through 1 month after Dose 2.

The primary endpoint "AEs from Dose 1 to 1 month after Dose 2" and other AE endpoints will be summarized by SOC and PT at the participant level.

This primary endpoint will be supported by summaries and listings of related AEs, severe AEs, and immediate AEs (within the first 30 minutes after each dose).

AE reporting will be based on the specific reporting period. Standard algorithms for handling missing AE dates will be applied as described in the Pfizer Vaccine data standard rules.

A 3-tier approach will be used to summarize AEs. Under this approach, AEs are classified into 1 of 3 tiers. Different analyses will be performed for different tiers:

- Tier 1 events: These are prespecified events of clinical importance and are identified in a list in the product's safety review plan.
- Tier 2 events: These are events that are not Tier 1 but are considered "relatively common." A MedDRA PT is defined as a Tier 2 event if there are at least 4 of participants with the AE term in at least 1 vaccine group.
- Tier 3 events: These are events that are neither Tier 1 nor Tier 2.

Confirmed COVID-19 diagnosis (SARS-CoV-2 positive test) will be collected as an AESI from the time the participant provides informed consent until study completion (Month 12 (Visit 9) for the clinical laboratory subset, Month 12 (Visit 7) for standard participants).

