# 6.3. Exploratory Endpoints

## 6.3.1. Immunogenicity Endpoints

#### 6.3.1.1. SARS-CoV-2 Serum Neutralizing Titers

# **6.3.1.1.1.** Subgroup Analyses for Participants With/Without Confirmed COVID-19 During the Study

Primary/secondary endpoints for SARS-CoV-2 serum neutralizing titer will be performed by subgroup of participants with/without confirmed COVID-19 during the study as described in Section 3.1.1. However, if the number of participants with confirmed COVID-19 during the study is less than 10, only listings will be displayed.

The definition to include participants for the subgroup analysis is described in Section 3.1.1.

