## 6.3.1.2. SARS-CoV-2 N-Binding Antibody

- Estimands:
  - Percentage of participants with seroconversion by N-binding antibody.
- Analysis set: Participants with seroconversion with/without confirmed COVID-19 during the study in evaluable and all-available immunogenicity populations (Section 4). However, if the number of participants with confirmed COVID-19 during the study is less than 10, the summary will be performed for the participants without confirmed COVID-19 during the study in evaluable and all-available immunogenicity populations (Section 4).
- Analysis time points: Baseline and 21 days after Dose 1; 7 and 14 days and 1, 6, and 12 months after Dose 2.
- Analysis methodology: Descriptive statistics (Section 5.2.1).
- Intercurrent events and missing data: Titers/concentrations below the LLOQ or denoted as BLQ will be set to 0.5 × LLOQ for analysis. However, this calculation may be adjusted based upon additional data from the assay. Missing data will not be imputed.
- Reporting results: Percentages of participants with seroconversion will be calculated with the associated 2-sided 95% CIs (Clopper-Pearson method) at each time point after vaccination.

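### In the exploratory COVID-19 subgroup, one label per participant is applied to every draw, so neutralizing-titer rows cannot be read as post-infection or infection-free responses

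*SAP*

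**What the plan says.** The exploratory objective in SAP 2.1 is "To describe the immune responses elicited by prophylactic BNT162 vaccine in participants with/without confirmed COVID-19 during the study". Protocol Section 3 carries the same objective.

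SAP 3.3.1 puts a participant in the confirmed group once for the whole study: members are "defined as those who reported confirmed COVID-19 diagnosis as an AESI by Visit 9 (clinical laboratory subset) or Visit 7 (standard participants"). The draws summarized under that label are "Baseline (only for GMTs), 21 days after Dose 1; 7 and 14 days and 1, 6 and 12 months after Dose 2". SAP 6.3.1.1.1 then says "Primary/secondary endpoints for SARS-CoV-2 serum neutralizing titer will be performed by subgroup of participants with/without confirmed COVID-19 during the study". With fewer than 10 confirmed cases it replaces the summary by listings. It sends the reader to Section 3.1.1 for the definition, which in fact stands in 3.3.1.

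The event behind the label is a positive test. SAP 3.1.1.4 states "Confirmed COVID-19 diagnosis (SARS-CoV-2 positive test) will be collected as an AESI". Swabs are scheduled only at the two vaccination visits (Protocol 8.15). For a later illness the site is told to "Collect local test results of COVID-19 and local diagnosis of COVID-19 as available" (Protocol 8.13.1).

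SAP 3.3.1 also defines N-binding seroconversion, but as an endpoint; it moves nobody between groups. SAP 6.3.1.2 reports seroconversion by the same confirmed/not-confirmed split. With fewer than 10 confirmed cases, "the summary will be performed for the participants without confirmed COVID-19 during the study in evaluable and all-available immunogenicity populations".

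**The concern.** Infection can change a titer only in samples drawn afterwards. Here an event at any time up to 12 months decides the row for samples already taken, including baseline. A participant diagnosed in month 10 contributes six pre-infection titers to the confirmed row and one post-infection titer.

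The other row has the opposite problem. After Dose 2 an infection without symptoms would be seen only through N-binding antibody or a chance local test. If only N-binding shows it, the participant's later titers stay in the not-confirmed GMT. Yet SAP 6.1.2.1.2 and 6.2.1.1.2 accept a positive N-binding result as evidence of infection at baseline.

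A reader comparing the two rows would expect to see what infection adds to the vaccine response. As defined, the early contrasts are diluted and the late not-confirmed GMT may be too high.

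**Working it through.** The plan states no expected figure for this analysis, so there is none to reproduce. The text settles the defect: no section ties the diagnosis date to the sample date. The arithmetic below only shows the possible size, and its rates and ratios are assumptions.

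**Draw days after Dose 1**, using nominal days or mid-window values from the schedule of activities: 0, 21, 28, 35, 52.5 (21 + 31.5), 182 (21 + 161) and 385 (21 + 364).

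**Confirmed row.** Assume onset is even over days 0 to 385 and infection multiplies the titer by a constant R from onset. The share already infected at day d is f = d/385, and the apparent ratio is R^f.

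- 1 month: f = 52.5/385 = 0.136. The apparent ratio is 2^0.136 = 1.10, 4^0.136 = 1.21 or 8^0.136 = 1.33.
- 6 months: f = 182/385 = 0.473. The apparent ratio is 2^0.473 = 1.39, 4^0.473 = 1.93 or 8^0.473 = 2.67.
- 12 months: f = 1, so the full R appears.
- Mean share of the seven samples taken before infection: 1 − (0 + 21 + 28 + 35 + 52.5 + 182 + 385)/(7 × 385) = 1 − 703.5/2695 = 0.74.

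For R = 4 the ratio would climb from 1.2 to 1.9 to 4 across visits only because cases accumulate.

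The evaluable set requires two doses, and Protocol 8.15 withholds Vaccination 2 after symptomatic confirmed COVID-19. Onset from day 21 on may therefore suit that set better: f = 31.5/364 = 0.087 and 161/364 = 0.442, so R = 4 appears as 1.13 and 1.85.

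**Not-confirmed row.** If a share s is silently infected with titer ratio R, the GMT is multiplied by R^s.

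- s = 1%, R = 5: 5^0.01 = 1.016; s = 5%, R = 10: 10^0.05 = 1.12.
- s = 5%, R = 4: 4^0.05 = 1.07; s = 20%, R = 4: 4^0.20 = 1.32.

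**The 10-case rule.** The expected evaluable population is 144 (Protocol 9.2), and 10/144 = 6.9%. The binomial probability of at least 10 cases is 0.07% at an assumed attack rate of 2%, 18.5% at 5%, 55.7% at 7% and 92% at 10%.

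**Crossover.** Visits 9 and 7 apply only to original BNT162b2 recipients and placebo recipients who decline the vaccine. For those who cross over, confirmed COVID-19 is collected to Visit 104 (Protocol 8.3.1), but the last scheduled immunogenicity draw is at Visit 101. SAP 3.3.1 names no cut-off for them.

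**The case against.** The strongest reply is that the split does what the objective asks. The objective concerns confirmed COVID-19 during the study, and the protocol lists the early draws under it. Keeping unconfirmed infections among the not-confirmed agrees with that wording. Grouping by later infection can also show whether future cases had different titers beforehand, which is a fair descriptive question. All of this stands. A reader might infer that neither group answers the objective; the documents do not support that.

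A reader might also infer that the trial's titer or persistence results are compromised. They are not: the 1-month primary and the 6- and 12-month secondary GMTs and GMFRs are reported unsplit (SAP 6.1.2.1.1 and 6.2.1.1.1). Only this exploratory analysis is sorted by the label, the study tests no hypotheses, and below 10 cases neither row is summarized for titers.

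Silent infection is partly visible, because SAP 6.3.1.2 reports seroconversion in the not-confirmed group. That shows its extent but does not take those samples out of the titer GMT.

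A tempting further step is to let N-binding define the groups everywhere. In 6.3.1.2 that would be circular, since seroconversion is the outcome there.

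The listing rule decides whether a table appears, not whether the rows mean what they seem to mean once it does.

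**Conclusion.** The point holds in a limited form. The grouping matches the objective, but the confirmed row mixes pre- and post-infection samples and the not-confirmed row is not infection-free. Neither can be read as a post-infection or infection-free response.

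Under even onset over 385 days, a 4-fold effect appears as about 1.2-fold at 1 month and 1.9-fold at 6 months. The not-confirmed GMT would be overstated by about 2% to 12% if 1% to 5% were silently infected with 5- to 10-fold titers, and by up to 32% if 20% were infected with 4-fold titers. Onset pattern, titer ratios and silent-infection rates are all assumed, and the ratio need not be equal in the two arms. Because the analysis is exploratory, descriptive and conditional on 10 cases, this is an inexpensive improvement, not a threat to the trial's main results.

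**What to change.** - In SAP 3.3.1 and 6.3.1.1.1, keep the confirmed/not-confirmed grouping. For neutralizing titers, flag each sample as before or after the positive-test date of the AESI. Summarize post-infection samples separately from samples taken before a later infection.
- Apply the 10-participant listing rule to each row at each visit.
- Add a sensitivity summary of the not-confirmed group that excludes samples drawn at or after N-binding seroconversion.
- Leave the grouping in 6.3.1.2 on confirmed COVID-19 alone.
- For placebo recipients who cross over, state that titers count up to the Visit 101 draw and that AESIs are counted up to that draw.
- Correct the reference in 6.3.1.1.1 from Section 3.1.1 to 3.3.1.

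The cost is SAP wording and a derived flag per sample. AESIs are already recorded, and N-binding is planned at every draw. I assume the positive-test date is held with the AESI record.

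The price is smaller groups that vary by visit, with more results shown only as listings. Under even onset, 10 post-infection samples would need about 73 confirmed cases at 1 month (10/0.136) and about 21 at 6 months (10/0.473).

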# 3.4. Baseline and Other Variables

Measurements or samples collected prior to Dose 1 are considered the baseline data for the assessments.

#### 3.4.1. Demographics, Medical History, and Physical Examination

The demographic variables are age at Dose 1 (in years), sex (male or female), race (Asian), racial designation (Japanese) and ethnicity (Hispanic/Latino, non-Hispanic/non-Latino, not reported).

Age at the time of vaccination (in years) will be derived based on the participant's birthday. For example, if the vaccination day is 1 day before the participant's 21st birthday, the participant is considered to be 20 years old. For participants who were randomized but not vaccinated, the randomization date will be used in place of the date of vaccination at Dose 1 for the age calculation. If the randomization date is also missing, then the informed consent date will be used for the age calculation.

Medical history will be categorized according to MedDRA.

If the baseline clinical assessment indicates that a physical examination is necessary to comprehensively evaluate the participant, physical examination will be performed and any findings recorded in the source documents and, if clinically significant, it will be recorded on the medical history CRF.

# 3.4.2. E-Diary Completion

An e-diary will be considered transmitted if any data for the local reactions, systemic events, or use of antipyretic medication are present for any day. If all data are missing for all items on the e-diary for all 7 days after vaccination, then the e-diary will be considered not transmitted. An e-diary will be considered completed if all expected data for all 7 days are available (ie, not missing). Otherwise, the e-diary will be considered incomplete. For any given day, an e-diary will be considered complete if all expected data are available.

#### 3.4.3. Prior/Concomitant Vaccines and Concomitant Medications

The following concomitant medications and vaccinations will be recorded in the CRF:

• All vaccinations received from 28 days prior to study enrollment until the 6-month follow-up visit (Visit 8 for clinical laboratory subset, Visit 6 for the other participants).

# 3.5. Safety Endpoints

Local reactions, systemic events, AEs, and SAEs have been described above in the primary safety endpoints.

# 4. ANALYSIS SETS (POPULATIONS FOR ANALYSIS)

Data for all participants will be assessed to determine if participants meet the criteria for inclusion in each analysis population prior to unblinding and releasing the database and classifications will be documented per SOPs.

Population	Description		
Enrolled	All participants who have a signed ICD.		
Randomized	All participants who are assigned a randomization number in the IWR system.		
Evaluable	All eligible randomized participants who receive 2 doses of the vaccine to which		
immunogenicity	they are randomly assigned, with Dose 2 received within the predefined window		
	(within 19-42 days after Dose 1), have at least 1 valid and determinate		
	immunogenicity result after Dose 2 from the blood collection within an appropriate		
	window after Dose 2 (within 28-42 days after Dose 2), and have no other important		
	protocol deviations as determined by the clinician.		
All-available	All randomized participants who receive at least 1 dose of the investigational		
immunogenicity	product with at least 1 valid immunogenicity result after vaccination. Participants		
	will be grouped as randomized in the immunogenicity analysis.		
Safety	All randomized participants who receive at least 1 dose of the study intervention.		
	Participants will be grouped according to the vaccine as administered in the safety		
	analysis.		

The important protocol deviations will be determined by the medical monitor. An important protocol deviation is a protocol deviation that, in the opinion of the sponsor's clinician, would materially affect assessment of immunogenicity/efficacy, (eg, participant receipt of a prohibited vaccine or medication that might affect immune response or a medication error with suspected decrease in potency of the vaccine). The sponsor's clinician will identify those participants with important protocol deviations that result in exclusion from analysis populations before primary analysis.

Both evaluable and all-available populations will be used for immunogenicity analyses. If there is less than a 10% difference in the total number of participants included between the all-available and evaluable populations, only the evaluable population will be used in the analysis of immunogenicity results.

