#### 6.3.3. Blinding of the Sponsor

To facilitate rapid review of data in real time, the majority of sponsor staff will be unblinded to study intervention allocation for all participants. All laboratory testing personnel performing serology assays will remain blinded to study intervention assigned/received throughout the study.

Those study team members who are involved in ensuring that protocol requirements for study intervention preparation, handling, allocation, and administration are fulfilled at the site will be unblinded for the duration of the study (eg, unblinded study manager, unblinded CRA). CRAs and study managers not involved in ensuring that protocol requirements for study intervention preparation, handling, allocation, and administration are fulfilled at the site will remain blinded to study intervention assigned/received throughout the study.

At the time when the original study intervention allocation for all participants will be unblinded by the site staff, all members of the study team including CRAs will become unblinded to the participant's original study intervention allocation.

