# 8.2.3. Surveillance of Events That Could Represent Enhanced COVID-19 Disease

As this is a sponsor open-label study, the sponsor will conduct unblinded reviews of the data during the course of the study, including for the purpose of safety assessment.

Participants will be surveilled for potential COVID-19 illness from Visit 1 onwards (see Section 8.13).

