# 5. GENERAL METHODOLOGY AND CONVENTIONS

To facilitate rapid review of data in real time, Sponsor staff will be unblinded to study intervention allocation. All laboratory testing personnel performing serology assays will remain blinded to study intervention assigned/received throughout the study. Further details can be found in protocol, Section 6.3. The timing for statistical analyses is specified in Section 7.

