#### 6.1.2. Immunogenicity Endpoints

The statistical analysis of immunogenicity results will be primarily based on the Evaluable immunogenicity populations as defined in the protocol, Section 9.3.

An additional analysis will be performed based on the all-available populations if there is a large enough difference in sample size between the all-available immunogenicity population and the evaluable immunogenicity population. Participants will be summarized according to the vaccine group to which they were randomized. Missing serology data will not be imputed.

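### SAP Section 4 relies on classification before unblinding in a study that is open-label to the sponsor, and its pooled 10% head-count rule can remove the all-available GMT and GMFR; the likely effect is small

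*SAP*

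**What the plan says.** **Classification.** SAP Section 4 plans to establish, from each person's data, "if participants meet the criteria for inclusion in each analysis population prior to unblinding and releasing the database and classifications will be documented per SOPs". Most evaluability criteria are objective: two doses as randomized, Dose 2 at 19 to 42 days, and a valid result from blood drawn 28 to 42 days after Dose 2. One is a judgement, the absence of other important protocol deviations. SAP Section 4 assigns that judgement to the medical monitor and to the sponsor's clinician, who is to "identify those participants with important protocol deviations that result in exclusion from analysis populations before primary analysis".

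**Blinding of the sponsor.** SAP Section 5: "Sponsor staff will be unblinded to study intervention allocation". Protocol Section 6.3.3: "the majority of sponsor staff will be unblinded to study intervention allocation for all participants". Protocol Section 8.2.3: "As this is a sponsor open-label study, the sponsor will conduct unblinded reviews of the data during the course of the study". The roles that protocol Section 6.3.3 keeps blinded are serology laboratory personnel and the CRAs and study managers who do not deal with product handling. When sites unblind under amendment 3, the whole study team becomes unblinded.

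**The all-available analysis.** SAP Section 4 uses only the evaluable population if there is "less than a 10% difference in the total number of participants included between the all-available and evaluable populations". SAP Section 6.1.2 gives the same condition without a number: "An additional analysis will be performed based on the all-available populations if there is a large enough difference in sample size". Protocol Section 9.4.1 also leaves it unquantified. SAP Sections 6.1.2.1.1 and 6.2.1.1.1 name both populations as the analysis set with no condition. The SAP's all-available population needs a dose of the investigational "product with at least 1 valid immunogenicity result after vaccination"; protocol Section 9.3 requires the result to come after Dose 2.

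**What is reported in any case.** SAP Section 6.4.2.1 tabulates exclusions from each population, with reasons, by vaccine group.

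**The concern.** A reader of SAP Section 4 would take classification before unblinding as a bias control on who enters the primary immunogenicity population. The rest of the plan does not supply that control on the sponsor side, where the judged exclusions are made. The requirements to act before the primary analysis and to document decisions set timing and traceability. They do not ensure that the deciding role has not seen allocation or titers.

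The all-available GMT and GMFR are the natural check on what the exclusions did to the primary estimates. Whether that check appears depends on a head count that pools the arms, ignores titers and has no stated denominator. At stake is how the primary GMT and GMFR are read. The study tests no hypothesis, so no error rate or power is affected.

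**Working it through.** **1. Blinding, by role.** Protocol Sections 6.3.2, 8.11.1.9 and 8.11.2.6 keep the investigator and the evaluating site staff blinded, with unblinding scheduled after the 1-month visit. Serology personnel are blinded throughout. The medical monitor and the sponsor's clinician appear in no list of blinded roles, and their individual status is not stated. The objective criteria leave little room for judgement, so the exposed step is the call on important deviations. Because the primary outputs are within-group GMT and GMFR, allocation alone does not show which exclusion would move an estimate; that takes knowledge of titers. The plan neither says that the deciding role sees titers first nor prevents it.

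**2. The plan's own figures.** Protocol Section 9.2 gives 160 randomized (120 vaccine, 40 placebo), about 10% nonevaluable, and an SD of 0.58 on the natural log scale.
- Evaluable: 160 × 0.90 = 144; 120 × 0.90 = 108; 40 × 0.90 = 36. All reproduce.
- Precision: exp(−1.982 × 0.58/√108) = 0.895, against the stated 90%.

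**3. Where the 10% rule cuts, if all 160 are all-available.**
- Denominator all-available: 16/160 = 10.0% keeps the table; 15/160 = 9.4% drops it.
- Denominator evaluable: 15/145 = 10.3% keeps it; 14/146 = 9.6% drops it.
- If one of the 16 planned nonevaluable participants is also not all-available, the difference is 15. Then 15/159 = 9.4% drops the table and 15/144 = 10.4% keeps it, so the unstated denominator decides.

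**4. Chance that the table is dropped.** X ~ Binomial(160, p), with all 160 assumed all-available:

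| Nonevaluable rate p | P(X ≤ 15), all-available denominator | P(X ≤ 14), evaluable denominator |
|---|---|---|
| 8% | 0.79 | 0.70 |
| 10% | 0.46 | 0.36 |
| 12% | 0.19 | 0.12 |

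Participants with no post-vaccination result are in neither population. They narrow the gap and make a drop more likely. Participants who are all-available but have no 1-month titer widen it and make a drop less likely.

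**5. Size of an unreported shift (illustration).** Of 15 exclusions unrelated to arm, 15 × 120/160 = 11.25 are expected among vaccinees (hypergeometric 95% range 8 to 14). Suppose k vaccinees are excluded, all with 1-month titers averaging g SDs below the mean of the 120. The evaluable GMT then exceeds the all-available GMT by the factor exp[k/(120 − k) × g × 0.58].

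| k | g = 0.25 | g = 0.5 | g = 1 |
|---|---|---|---|
| 4 | 1.005 | 1.010 | 1.020 |
| 11 | 1.015 | 1.030 | 1.060 |
| 15 | 1.021 | 1.042 | 1.086 |

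The last row needs all 15 exclusions to be vaccinees, a chance of about 1% (0.0106) if exclusion is unrelated to arm. The values of g are assumptions; the documents give no titers for excluded participants. These counts cover exclusions of every kind, so judged exclusions alone would move the GMT less.

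**The case against.** The best defence has four parts.

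- **Blinding.** The data behind most exclusions (dose dates, blood draws, prohibited medication) are recorded up to the 1-month visit largely by blinded site staff, and the assays are run blind. Sponsor unblinding is disclosed openly. Elsewhere in SAP Sections 6.4.2.1, 6.4.3.1 and 6.4.5, unblinding means the amendment 3 event, so the phrase in Section 4 may have meant that or database release. The blinding of site and laboratory stands. The other possible meanings do not rescue the sentence as a bias control, because neither keeps allocation from the sponsor.
- **Prespecification.** A numeric threshold for the protocol's undefined condition limits discretion after the fact. That is a real merit, but without a denominator the number is not fully specified.
- **Visibility.** Exclusion counts and reasons by arm are reported whatever the head count. This stands: an imbalance in numbers cannot be hidden. Counts do not show how the GMT or GMFR moved.
- **Size.** At the expected arm split, the illustrated shifts stay below the distance from the GMT to its lower confidence limit. This also stands, and it is why the point is minor.

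A reader might infer that staff who know the arm can steer the primary estimates. The documents do not support that: no between-group GMT comparison is planned, arm alone does not identify a low titer, and nothing says the clinician sees titers before deciding. A reader might also think that counting people without a 1-month titer as all-available helps to suppress the table. It works the other way, because it widens the gap.

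**Conclusion.** The point holds in a limited form and is minor. SAP Section 4 describes a safeguard that the sponsor-side blinding arrangements do not provide. The exposure covers judged exclusions only, and it arises only if the deciding role can see post-vaccination titers. No actual bias is shown.

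The 10% rule is a separate weakness. It sits on the plan's own nonevaluable rate, lacks a denominator, and fits poorly with SAP Sections 6.1.2.1.1 and 6.2.1.1.1, which list both populations without condition. At a 10% rate the all-available table is close to a coin toss (46% or 36% chance of being dropped).

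The consequence is an illustrative rise of 1.5% to 6.0% in the vaccine GMT for 11 vaccinee exclusions, against planned precision of about 10%. It is zero if exclusions are unrelated to titer or have no 1-month sample, since missing results are not imputed. These figures rest on the plan's SD of 0.58, on all 160 being all-available and on assumed titer deficits.

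**What to change.** 1. In SAP Section 4, replace the reference to unblinding with a statement that judged exclusions are settled and documented before post-vaccination titers are released to the role that decides them.
2. Report the all-available GMT and GMFR as a supportive table whatever the head count. Amend SAP Sections 4 and 6.1.2 accordingly and note the change from protocol Section 9.4.1. The evaluable population stays primary, and the missing denominator no longer matters.

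The cost is wording edits and one extra table, which SAP Sections 6.1.2.1.1 and 6.2.1.1.1 already list. SAP Section 4 already requires the classifications to be documented.
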